## **5.6 Criteria for Removal from Study**

Patients will be removed from treatment when any of the criteria listed in Section 5.4 applies. The reason for study removal and the date the patient was removed must be documented in the Case Report Form.

Subjects/patients may withdraw at any time or be dropped from the study at the discretion of the investigator should any untoward effects occur. In addition, a subject/patient may be withdrawn by the investigator if he/she violates the study plan or for administrative and/or other safety reasons. The investigator or study coordinator will notify the appropriate parties within 2 business days when a subject has been discontinued/ withdrawn due to an adverse event (Section 7). When a subject discontinues/withdraws prior to study completion, all applicable activities scheduled for the final study visit should be performed at the time of discontinuation. Any adverse events present at the time of discontinuation/withdrawal will be followed until resolution.

# **6. DOSING DELAYS/DOSE MODIFICATIONS**

## **6.1 Dose Delays**

- Study drugs can be administered within 48 hours of their scheduled time.
- Study drugs will be held for DLTs until adverse event returns to  $\leq$  Grade 2
- If interruption lasts for more than 14 days, study treatment will be discontinued.

## **6.2 Resuming Administration of Study Drug**

For toxicities that can be treated or prevented, such as nausea, vomiting, diarrhea and neutropenia, mucositis, treatment may be resumed at the previous dose once supportive measures have been instituted and toxicity recovers to Grade 2 or less.

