## **5.2 Dose-Limiting Toxicity**

A dose limiting toxicity (DLT) is defined as any toxicity not specifically included in section 5.2 that occurs within cycle 1 and is considered at least "possibly related to study drug administration." DLT is also defined as any toxicity possibly related to drug, occurring up to 7 days after completion of cycle 1 that results in a delay of initiating cycle 2. For patients who discontinue study drug administration after Cycle 1, DLT will be defined as any toxicity not specifically included in section 5.2 that occurs within 30 days of the last dose of drug on study, in cycle 1 that is considered at least possibly related to study

drug.

DLTs include:

- Hematologic dose-limiting toxicity will be defined as either Grade 4 neutropenia that does not resolve to  $\leq$  Grade 2 within  $\leq$  7 days, any Grade 4 thrombocytopenia, or any Grade 5 hematologic toxicity. At least three patients in each cohort must be evaluable for hematologic toxicity.
- Non-hematologic dose-limiting toxicity will be defined as any Grade 3, 4 or 5 non-hematologic toxicity, with the specific exception of:
- Grade 3 nausea or Grade 3 vomiting that in the opinion of the investigator occurs in the setting of inadequate compliance with supportive care measures specified in Section 5.1.7 and lasts for less than 48 hours.
- Grade 3 diarrhea that in the opinion of the Investigator occurs in the setting of inadequate compliance with supportive care measures specified in Section 5.1.7 and lasts for less than 48 hours.
- Grade 3 dehydration that, in the opinion of the investigator, occurs in the setting of inadequate compliance with supportive care measures specified in Section 5.1.7 and lasts for less than 48 hours.
- Grade 3 acidosis or alkalosis that responds to medical intervention by returning to  $\leq$  Grade 2 within 48 hours.
- Isolated (i.e. no other abnormalities) Grade 3 elevation of liver function tests (LFTs) without associated clinical symptoms, lasting for  $\leq$  5 days in duration.
- Isolated (i.e. no other abnormalities) Grade 3 elevation of amylase without associated clinical symptoms, lasting  $\leq$  5 days
- Grade 3 hypocalcemia, hypokalemia, hypomagnesemia, hyponatremia, or hypophosphatemia that responds to medical intervention.
- Grade 3 hypercholesterolemia.
- Grade 3 hypertriglyceridemia
- Grade 2 Alopecia
- Grade 3 Constipation
- Grade 3 Fatigue

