#### Romidepsin dose modification for Other Non-Hematologic and Hematologic Toxicities

All previously established or new toxicities observed any time, with the exception of those mentioned above, are to be managed as summarized in Table 8:

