**TABLE 8: Dose Modifications for Romidepsin**

Dose Modifications for Romidepsin	
CTCAE Grade or Abnormal Value	Romidepsin
Thrombocytopenia	
Grade 1 ( $75 \times 10^9/L - < LLN$ ) Grade 2 ( $50 - < 75 \times 10^9/L$ )	Maintain dose level Maintain dose level
Grade 3 or 4 thrombocytopenia:  OR  Thrombocytopenia that requires platelet transfusion or recurrent Grade 3 or 4 thrombocytopenia	Hold subsequent doses of therapy until thrombocytopenia returns to $\leq$ Grade 2 or baseline and continue at full dose  Hold subsequent doses of therapy until thrombocytopenia returns to $\leq$ Grade 2 or baseline and permanently reduce dose of romidepsin to the next reduced level below.. If the same toxicity recurs despite dose reduction, patients should be taken off study.
Neutropenia (ANC)	
Grade 1 ( $1.5 \times 10^9/L - < LLN$ ) Grade 2 ( $1.0 - < 1.5 \times 10^9/L$ )	Maintain dose level Maintain dose level
Grade 3 and 4 neutropenia:	Hold subsequent doses of therapy until specific cytopenia returns to $\leq$ Grade 1 or baseline and continue at full dose
Febrile Neutropenia	
Febrile ( $\geq 38.5^{\circ}C$ ) Grade 4 neutropenia or recurrent Grade 3 or 4 neutropenia:	Hold subsequent doses of therapy until neutropenia returns to $\leq$ Grade 1 or baseline and permanently reduce dose of romidepsin to the next reduced level below.. If the same toxicity recurs despite dose reduction, patients should be taken off study
All Other Non-Hematologic Drug Toxicities (not mentioned in previous tables)	
Grade 1 or 2:	Maintain dose level
Grade 3	Hold treatment with romidepsin until toxicity returns to $\leq$ Grade 1 or baseline, then restart therapy at full dose. If Grade 3 toxicity recurs, reduce dose of romidepsin to the next reduced level below.. This is a permanent dose reduction.
Grade 4	Grade 4 toxicity: Hold treatment with romidepsin until toxicity returns to $\leq$ Grade 1 or baseline, and then restart therapy at the next reduced level below.. This is a permanent dose reduction

Dose interruption or study discontinuation is not required for lymphopenia of any grade.

In general, if study drug has been held and the toxicity does not resolve, as defined above, then drug must

be discontinued.

Note: Dose reductions should not be performed for alopecia or for nausea or vomiting that was not treated with aggressive anti-emetic support.

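### After neutropenia, Section 6.2 lets romidepsin resume at the previous dose where the Section 6.3.1 table requires a longer hold and sometimes a permanent reduction, and no text says which rule prevails

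*Combined protocol and SAP*

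**What the plan says.** **Section 6.2** covers toxicities that can be treated or prevented and names nausea, vomiting, diarrhea, neutropenia and mucositis. For these, "treatment may be resumed at the previous dose once supportive measures have been instituted and toxicity recovers to Grade 2 or less". It does not separate the two drugs and contains no reduction.

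**Section 6.1** sets a general hold: "Study drugs will be held for DLTs until adverse event returns to" Grade 2 or below. It also gives a dosing window, "Study drugs can be administered within 48 hours of their scheduled time", and ends treatment if an interruption exceeds 14 days.

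**Section 6.3.1** introduces Table 8 as covering all toxicities at any time, "with the exception of those mentioned above, are to be managed as summarized in Table 8". The table sets these romidepsin rules:
- Grade 3 or 4 neutropenia: hold until at or below "Grade 1 or baseline and continue at full dose".
- Febrile Grade 4, or recurrent Grade 3 or 4, neutropenia: hold until at or below "Grade 1 or baseline and permanently reduce dose of romidepsin to the next reduced level below".
- Grade 3 non-hematologic toxicity: hold until at or below "Grade 1 or baseline, then restart therapy at full dose", with a permanent reduction if it recurs.
- Grade 4 non-hematologic toxicity: the same recovery level, then a permanent reduction.

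**Section 5.1.3** sets criteria before each treatment, including an ANC above 1000 and recovery of drug-related non-hematologic toxicity to Grade 1, with an exception where otherwise indicated.

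**Section 5.1.6** calls for immediate reduction after Grade 4 toxicity in Phase II. For hematologic events with a missed dose, it leaves reduction to the physician's discretion.

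**Section 5.1.4** says that missed doses are not made up.

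**The concern.** Sections 6.2 and 6.3.1 govern the same decision for the same patient: when to give romidepsin again after neutropenia, and at what dose. They answer differently, and no sentence sets an order between them. A treating physician who follows 6.2 as written can give the previous dose to a patient whose dose Table 8 says must be permanently lowered. That patient also stays outside Table 8's next step, which takes patients off study if the same toxicity recurs despite reduction. Two patients with the same event could be managed differently, each within the protocol. This is a contradiction between two safety rules, not a missing detail.

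**Working it through.** The point rests on comparing text, and the plan states no figure to reproduce. The rules for romidepsin, side by side:

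| Event | Section 6.2 | Table 8, Section 6.3.1 | Other text | Result |
|---|---|---|---|---|
| First, non-febrile Grade 3/4 neutropenia | Grade 2 or less, previous dose | Grade 1 or baseline, full dose | 5.1.3: ANC above 1000 | Threshold differs, dose agrees |
| Febrile Grade 4 or recurrent Grade 3/4 neutropenia | Grade 2 or less, previous dose | Grade 1 or baseline, permanent reduction | 5.1.6: hematologic reduction discretionary | Threshold and dose differ |
| Grade 4 non-hematologic (treatable) | Grade 2 or less, previous dose | Grade 1 or baseline, permanent reduction | 5.1.3: Grade 1; 5.1.6: reduce at once (Phase II) | Dose differs; threshold largely settled by 5.1.3 |
| First Grade 3 non-hematologic (treatable) | Grade 2 or less, previous dose | Grade 1 or baseline, full dose | 5.1.3: Grade 1 | Threshold largely settled by 5.1.3 |
| Grade 3/4 thrombocytopenia | Not named | Grade 2 or baseline | | No threshold conflict |
| Grade 2 neutropenia only | | Maintain dose | | No conflict |

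**Where the thresholds part.** Table 8 defines Grade 2 neutropenia as ANC 1.0 to <1.5 x10^9/L. A patient recovering from Grade 3/4 into that band, with a better baseline, may be dosed under 6.2 and must be held under Table 8. Section 5.1.3 prints its ANC floor per dL. Read as per microlitre (my assumption), it is 1.0 x10^9/L, the bottom of the same band. It is a necessary condition, so it does not contradict Table 8, but it gives no support for waiting until 1.5.

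**Reach of 6.1.** Its Grade 2 rule applies to DLTs. In Section 5.2, "Hematologic dose-limiting toxicity will be defined as either Grade 4 neutropenia that does not resolve to" Grade 2 or below within 7 days. Grade 3 neutropenia and quickly resolving Grade 4 neutropenia are therefore outside it, and the neutropenia conflict is mainly 6.2 against Table 8.

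**Search for an order of precedence.** Table 8's lead-in excepts toxicities mentioned above, which most naturally means the cardiac events of Table 7. It does not name 6.2. The opening of Section 6.3 points to the romidepsin package insert or the (de)escalation tables and does not rank either against 6.2.

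**What the dose difference could be, conditionally.** Full Phase II romidepsin is 3 x 14 = 42 mg/m2 per 35 days, or 42/5 = 8.4 mg/m2/week.
- If a hold costs one dose: 28/5 = 5.6 mg/m2/week, and 5.6/8.4 = 0.667, or -33% for that cycle. This requires the hold to outlast the 48-hour window and the dose to be treated as missed.
- If Table 8's next lower level is the first Phase II step in 5.1.6 (14 mg/m2 on Days 8 and 15 every 28 days): 28/4 = 7.0 mg/m2/week, and 7.0/8.4 = 0.833, or -16.7%.
- That same step keeps azacitidine at 300 mg x 14 = 4200 mg but shortens the cycle. Weekly azacitidine goes from 4200/5 = 840 mg to 4200/4 = 1050 mg, and 1050/840 = 1.25, or +25%.

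**The case against.** The strongest reply is that the text mostly resolves itself. Section 6.2 is permissive, whereas Table 8 is mandatory, specific to romidepsin, and introduced as covering all toxicities at any time. A physician who follows Table 8 breaches nothing in 6.2. This is a good reason to think Table 8 is meant to govern. It does not dispose of the point, because a physician who uses the permission in 6.2 is also following the protocol, and 5.1.3 and 5.1.6 lend that choice support.

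The second reply is that the disputed ANC band is not inherently unsafe. Entry requires an ANC of at least 1,000, the pre-dose check accepts anything above 1000, and Table 8 itself maintains the dose for Grade 2 neutropenia. Neither rule permits resumption while neutropenia is still Grade 3 or 4. This stands, and it makes the threshold difference secondary. It does not touch the permanent-reduction cases.

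Third, the non-hematologic side is weaker. Section 5.1.3 already asks for Grade 1, although its exception could be read to admit 6.2. Section 5.1.6 sides with Table 8 on reduction after Grade 4 toxicity. Table 8 also bars reduction for nausea or vomiting that was not treated aggressively. All of this stands.

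Fourth, Section 13.1 describes Phase I as single-institution, and nothing describes further sites for Phase II. Divergent practice is then less likely, but still possible between physicians.

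**Conclusion.** The conflict is real and limited. For romidepsin after febrile Grade 4 or recurrent Grade 3/4 neutropenia, and after a treatable Grade 4 non-hematologic toxicity, Section 6.2 permits a dose that Table 8 forbids. After any Grade 3/4 neutropenia, the two also differ on when dosing may restart. It should be corrected because it concerns patient safety and wording alone resolves it.

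A reader might infer three stronger things that the documents do not support:
- **That each affected patient loses a third of the cycle's romidepsin.** Section 6.1 tolerates interruptions of up to 14 days, so a hold may be a delay. The loss arises only under the two conditions given with the calculation.
- **That 8.4 against 7.0 mg/m2/week measures over-dosing.** Table 8 does not define its next lower level. The step in 5.1.6 lowers romidepsin by 16.7% while raising weekly azacitidine by 25%.
- **That the Phase I rate gives the frequency.** Section 2.4.2 reports Grade 3/4 febrile neutropenia in 19.2% of 26 patients across all dose levels, and no toxicities at the MTD. It shows that such events occur with this combination but gives no Phase II rate.

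The two-stage design is unaffected: N = 24, alpha and power stay as they are.

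**What to change.** Add to Section 6.2:

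> For romidepsin, the resumption threshold and dose follow Section 6.3.1 (Table 7 for cardiac events, the romidepsin dose-modification Table 8 for all others); where these are stricter than this section, they prevail. The pre-treatment criteria in 5.1.3 continue to apply to both drugs, and the physician may reduce further under 5.1.6.

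Make the Grade 2 hold rule in Section 6.1 subject to the same sentence. The section number is needed because the label Table 8 is used again for the reporting exclusions in Section 7.4.2. Naming Table 7 preserves the separate rule for cardiac events, under which romidepsin restarts at a reduced level only once the finding has resolved. The reference to 5.1.6 keeps open a reduction after a first Grade 4 neutropenia, where Table 8 alone would return to full dose.

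The amendment should not set a Grade 2 resumption threshold for azacitidine. That would be a new clinical rule, and it could serve as the exception that loosens the Grade 1 requirement in 5.1.3.

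The cost is a short wording amendment. An occasional romidepsin dose will be held longer, and may be lost, or will be given at a reduced level. Sample size, alpha and power do not change.

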#### 5.1.6 Dose De-escalation Decision Rules:

If a DLT is reached in the first cycle for a given patient, then the previous dose level will be utilized for that particular patient in subsequent cycles. Should that patient experience a second DLT at that lower dose, they will be removed from the study. Dose-escalation will resume until the maximally administered dose is achieved or MTD is reached.

For example, according to the schema in Table 2, if DLT is reached at dose level 1 (romidepsin 10 mg/m^2 and oral 5-azacitidine 100 mg/m^2), the frequency of romidepsin will be reduced to a Day 8 only dose. Dose escalation can resume starting at that point according to dose escalation rules (Table 3). The same

applies if DLT is reached at all other levels prior to dose level four.

Toxicities in cycles 2 and following may be accommodated by treating patients at one dose level below the present cohort. Toxicity in cycles 2 and beyond will not affect dose escalation for future patients.

In the Phase 2, de-escalation should follow the Phase 1 escalation guidelines. For instance, any recurrent Grade 3 toxicity, up to 3 de-escalations will be allowed, with the doses of the drugs being reduced to that described in Cohort 5 (azacytidine 300 mg Day 1-14, and romidepsin 14 mg/m^2 Day 8 and 15 every 28 days) → Cohort 4 (azacytidine 300 mg Day 1-14, and romidepsin 10 mg/m^2 Day 8 and 15 every 28 days) and then Cohort 3 (azacytidine 200 mg Day 1-14, and romidepsin 10 mg/m^2 Day 8 and 15 every 28 days). Any patient experiencing a Grade 4 toxicity should just be immediately dose reduced according to the guideline above. In addition, patients can be dose reduced per the treating physicians discretion.

Specifically, for hematologic toxicities, patients may receive GCSF for neutropenia. For cases where patients miss a dose secondary to a recurrent Grade 3 ANC or platelet count, or Grade 4 hematologic toxicity, dose reductions should occur as noted above at the physicians discretion (i.e. reduce to Cohort 5, then 4 then 3).

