## 6.3 Dose Modifications

If oral 5-azacitidine and romidepsin administration leads to a DLT beyond cycle 1 at a given dose level, dose modifications will occur in accordance with the drugs' FDA approved package insert for romidepsin, or as outlined in the dose (de)escalation tables. These post Cycle 1 DLTs will not count towards the overall determination of MAD & MTD for this study.

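### Section 6.2 allows a restart at the previous dose after toxicities for which Table 8 in Section 6.3.1, and in part Section 5.1.6, requires a reduction, and no text says which rule governs

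*Combined protocol and SAP*

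**What the plan says.** - **Section 6.2** covers treatable or preventable toxicities and names nausea, vomiting, diarrhea, neutropenia and mucositis as examples. For these, "treatment may be resumed at the previous dose once supportive measures have been instituted" and "toxicity recovers to Grade 2 or less". Those are its only conditions. It does not mention severity at onset, recurrence, fever, cycle or phase.
- **Section 6.3.1, Table 8** governs romidepsin. Its lead-in reads: "All previously established or new toxicities observed any time, with the exception of those mentioned above, are to be managed as summarized in Table 8". For Grade 4 non-hematologic toxicity the patient must recover to Grade 1 or baseline "and then restart therapy at the next reduced level below.. This is a permanent dose reduction". Recurrent Grade 3 non-hematologic toxicity, febrile Grade 4 neutropenia and recurrent Grade 3/4 neutropenia also lead to a permanent reduction. A closing note exempts nausea or vomiting that did not receive aggressive anti-emetic treatment.
- **Section 5.1.6** says of a first-cycle DLT: "then the previous dose level will be utilized for that particular patient in subsequent cycles". For Phase 2 it says: "Any patient experiencing a Grade 4 toxicity should just be immediately dose reduced according to the guideline above". Its next paragraph allows G-CSF for neutropenia. Where a dose is missed through recurrent Grade 3 ANC or platelet toxicity, or Grade 4 hematologic toxicity, it leaves the reduction to the physician.
- **Section 5.2** sets the DLT definition: "Non-hematologic dose-limiting toxicity will be defined as any Grade 3, 4 or 5 non-hematologic toxicity, with the specific exception of" a list of exemptions that follows.
- **Section 6.3** adds that if treatment "leads to a DLT beyond cycle 1 at a given dose level, dose modifications will occur", following either the romidepsin package insert or the (de)escalation tables.

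**The concern.** Several of the events that 6.2 names are events for which another section orders a lower dose. An investigator who relies on 6.2 alone could restart full-dose romidepsin in a patient for whom Table 8 requires a permanent reduction, and could do so at a lesser degree of recovery. That investigator would comply with one section and deviate from another.

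The decision at stake is re-exposure after severe toxicity. A secondary consequence is that recorded dose reductions and delays would depend partly on which section each treating physician used.

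**Working it through.** No arithmetic underlies the point. The check sets the rules side by side.

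**Dose on restart**

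| Event | Section 6.2 | Table 8 (romidepsin) | Section 5.1.6 |
|---|---|---|---|
| First Grade 4 diarrhea or mucositis | Previous dose allowed | Permanent reduction | Phase 2: immediate reduction. Cycle 1 DLT: lower level |
| Recurrent Grade 3 diarrhea or mucositis | Previous dose allowed | Permanent reduction | Phase 2: de-escalate, up to three steps |
| Grade 4 or recurrent Grade 3 nausea or vomiting | Previous dose allowed | Permanent reduction, unless anti-emetic support was not aggressive | As the two rows above |
| Febrile Grade 4 neutropenia | Previous dose allowed (by inference: neutropenia is named, fever is not mentioned) | Permanent reduction; off study if it recurs despite that | Phase 2: general Grade 4 rule, but discretionary if a dose was missed |
| Recurrent Grade 3/4 neutropenia (read as a trigger separate from fever) | Previous dose allowed | Permanent reduction; off study if it recurs despite that | Phase 2: discretionary if a dose was missed |
| First non-febrile Grade 4 neutropenia | Previous dose allowed | Full dose | Phase 2: general Grade 4 rule, but discretionary if a dose was missed |
| First Grade 3 non-hematologic event after cycle 1 | Previous dose allowed | Full dose | Phase 2: no reduction until it recurs |

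The first five rows conflict with Table 8 on dose, apart from the exempted nausea or vomiting. The last two do not. The clearest conflict is Grade 4 or recurrent Grade 3 diarrhea or mucositis: 6.2 names both, Table 8 has no exemption for them, and the discretionary paragraph in 5.1.6 does not reach them.

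**Search for a rule of precedence**

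1. The Table 8 lead-in is mandatory, whereas 6.2 is permissive. Its exception for events mentioned above follows directly after the cardiac table (Table 7) and most naturally means cardiac events. It does not name 6.2.
2. Section 6.3 offers two sources for later DLTs without ranking them and does not mention 6.2.
3. The sentence closing Section 5.2 sends the reader to Section 6 as a whole, which contains both rules.

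None of these states that Table 8 or 5.1.6 overrides 6.2.

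**Recovery grade before restart**

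| Place | Non-hematologic | Neutropenia |
|---|---|---|
| 5.1.3 | Grade 1, unless indicated otherwise | ANC above 1000 |
| 6.1 (DLT holds) | Grade 2 | Grade 2 |
| 6.2 | Grade 2 | Grade 2 |
| Table 8 (after Grade 3 or 4) | Grade 1 or baseline | Grade 1 or baseline |

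Section 5.1.3 prints the ANC limit per dL. I assume that per microliter is meant: 1000 per µL × 10^6 µL per L = 1.0 × 10^9/L, the lower end of Grade 2 in Table 8 (1.0 to below 1.5 × 10^9/L). On that reading, 5.1.3, 6.1 and 6.2 agree for neutropenia and Table 8 stands alone. For non-hematologic toxicity, 5.1.3 and Table 8 sit on one side and 6.1 and 6.2 on the other.

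**The case against.** The strongest reply is that nothing forces a contradiction on dose. Section 6.2 grants a permission and Table 8 gives a grade-specific instruction, so a site that follows Table 8 obeys both. One can also read 6.2 narrowly. Its condition that supportive measures be started echoes the DLT exemptions in 5.2 for short Grade 3 nausea, vomiting, diarrhea and dehydration under poor supportive-care compliance, and echoes Table 8's anti-emetic note. On that reading, 6.2 concerns under-supported events and not Grade 4 or recurrent ones.

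Much of this stands. It is why Table 8 is the likelier rule for romidepsin. But the narrow reading is not written down. Preferring the specific rule to the general one does not settle the matter either, because 6.2 names diarrhea and mucositis while Table 8 reaches them only through a catch-all row. A permission to restart at full dose still clashes with a mandatory reduction when both cover the same patient.

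Two further objections also stand. A reader might infer that 5.1.6 makes reduction compulsory for Phase 2 Grade 4 neutropenia. Its next paragraph gives the physician discretion where a dose was missed, so for neutropenia 5.1.6 is largely compatible with 6.2. A reader might also infer that 6.2 alone has the wrong recovery grade. Section 6.1 uses the same grade, and for neutropenia so in effect does 5.1.3.

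**Conclusion.** The plan contains overlapping restart rules with different dose consequences and no stated order of precedence. The conflict with Table 8 is firm for Grade 4 or recurrent Grade 3 diarrhea and mucositis, for nausea and vomiting at those grades when anti-emetic support was aggressive, and for recurrent Grade 3/4 neutropenia. For febrile Grade 4 neutropenia it rests on inference. The conflict with 5.1.6 is firm for cycle 1 DLTs and Phase 2 Grade 4 non-hematologic events, and weak for Phase 2 hematologic events. The recovery-grade mismatch is a separate inconsistency spread over four places.

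The text does not support saying that 6.2 overrides Table 8, or that sites would generally follow 6.2. Nor can a patient rate be given. The toxicity percentages in Section 2.4.2 pool all Phase I dose levels, and the same section reports no toxicities at the MTD, which is the Phase 2 dose. Phase I dose finding is reported there as complete, which limits the future reach of the cycle 1 rule. The Phase 2 sample size and error rates do not depend on this point. It should be corrected because it bears on patient safety and is cheap to fix.

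**What to change.** **Dose.** Reword 6.2 along these lines:

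> Treatment may restart at the same dose as before the hold, except where Section 5.1.6 or Section 6.3.1 (Tables 7 and 8) requires a dose reduction or removal from study, in which case that rule applies.

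Naming the dose before the hold avoids a clash of terms, since 5.1.6 uses the previous dose level to mean the next lower one. Keep the section number, because the reporting-exclusions table in 7.4.2 is also numbered 8.

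**Recovery grade.** Align 5.1.3, 6.1, 6.2 and Table 8 as a separate edit. For non-hematologic toxicity, put Grade 1 or baseline into 6.1 and 6.2, as in Table 8; 5.1.3 already has Grade 1 and needs only the baseline alternative. For neutropenia, choose one threshold and state it in all four places. The choice is clinical, between the Grade 2 that three sections accept and Table 8's Grade 1 or baseline.

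**What this leaves open.** Differences between 5.1.6 and Table 8 remain, such as three permitted de-escalations against removal after a recurrence. Table 8 covers romidepsin only, so the azacitidine dose after such an event should also be stated.

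**Cost.** A clause in 6.2 and matching edits to the recovery thresholds, with no added patients, procedures or data fields. Some patients will be reduced or held longer. Because 6.1 ends treatment after an interruption of more than 14 days, a stricter recovery grade may lead some to discontinue sooner. For neutropenia this would apply if Table 8's threshold is chosen and a patient's ANC stays in the Grade 2 range with a higher baseline.
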